6.4. Informed consent process

Informed consent will be obtained from every subject in writing by the Investigator or his authorized designee before the clinical Research is started. The subject will be informed both orally and in writing about all aspects that are relevant to the subject's decision to participate in the trial, including the trial procedures and risks and benefits of participation in the clinical Research. The informed consent will include an explanation of the study, duration, explanation of medical record access and patient anonymity, and how their coded data may be transferred, used for publications or in submissions for reimbursement support. The informed consent form will contain language that is non-technical and understandable to the patient.

Ample time should be provided for the subject to read and understand the informed consent form and to consider participation. The informed consent will include personally dated signatures of the subject and the principal investigator or an authorized designee responsible for conducting the informed consent process. The investigator or an appropriately designated member of the study staff shall co-sign the consent form, indicating they believe the subject has understood the nature and risks of the study and, in their estimation, the subject clearly understands the scope of the consent. The investigator must inform subjects that they are in a clinical trial, apprise them of their rights as set forth in the informed consent document, and make written documentation that such a discussion took place. The subject will receive a copy of the signed informed consent and any other written information.

IGT Systems	Clinical Research Protocol Next Generation X-ray Imaging System (NEXIS)	Doc ID: XCY612-130814 Rev: 01 Page 25 of 57
-------------	----------------------------------------------------------------------------	---------------------------------------------------

If new information becomes available that might significantly affect the subject's future health and medical care, it shall be provided to the subjects in written form. If relevant, subject shall be asked to reconfirm their continuing informed consent in writing. In this trial only patients that can give informed consent themselves will be included.

The procedure around how the informed consent is collected will be recorded in each subjects' medical record. The signed consent forms will be retained by the investigator and made available (for review only) to the study monitor and auditor on request.

The Investigation site will maintain a log of all screened patients detailing the reasons for any subsequent patient exclusions or non-participation in the study.

6.4.1. Subject withdrawal or discontinuation

Participation in this investigation is voluntary, and the subject may withdraw at any time. All enrolled subjects will be included in data analysis, unless they withdraw permission for their data to be used. The Sponsor will retain and continue to use any data collected prior to the withdrawal of consent, unless specified by the Subject.

In the event the subject chooses to withdraw, he/she will be instructed to contact the Investigator immediately. Withdrawal from the investigation will not affect the subject's standard of care. The subject will be informed of any significant information regarding new findings that may develop during the course of the research study that may relate to his or her willingness to continue participation as a study subject.

Subjects will participate in their routine follow-up (day 2, when applicable) and allow this data to be gathered. If their participation is terminated, any of their data which has been already gathered will continue to be included. The completion of a subject's participation in the study or early departure from the study must be fully documented in the subject's study progress notes.

Subjects will be considered discontinued from the study if any of the following occur:

- Subject voluntarily withdraws from the study: A subject may withdraw consent from study participation at any time.
- Subject withdrawn from the study by the investigator. An investigator may withdraw an enrolled subject from the study for the following reason:

If participation in the study is life threatening for the subject or at the investigator's own discretion.

6.5. Investigational device exposure and comparators

As per clinic standard, patients with suspected ischemic stroke are evaluated with neCT, mCTA and CTP upon admission. Patients arriving from another hospital with a confirmed LVO can optionally be imaged with only neCT and CTP. Also, as per clinic standard, ischemic stroke patients treated in any way (thrombolysis and/or thrombectomy) undergoes DECT 12-36 hours after treatment to assess the presence and extent of hemorrhage and ischemia. Patients diagnosed with hemorrhagic stroke will typically be evaluated with neCT and mCTA/CTA upon admission.

This study will investigate the performance of DE-CBCT in comparison to regular neCT/mCTA/CTA/CTP imaging at admission and subsequent DECT (DECT only for subjects in 3.I and 3.II). Table 3 provides an overview of the devices each subject is exposed to depending on inclusion criterion.

IGT Systems	Clinical Research Protocol	Doc ID: XCY612-130814 Rev: 01 Page 26 of 57
	Next Generation X-ray Imaging System (NEXIS)	

	Day 1	Day 2						
Inclusion criterion	Standard imaging (CT-based)	Iodine contrast eligibility test	DE-CBCT w/o contrast agent	DE-CBCT w contrast agent	Iodine contrast eligibility test	Standard imaging (DECT)	DE-CBCT w/o contrast agent	DE-CBCT w contrast agent
3.I	X	X	X	X ¹	X	X ²	X	X ¹
3.II	X				X	X	X	X ¹
3.III	X	X	X	X ¹				

Table 3. Overview of the devices the subject is exposed to depending on inclusion criterion. Timeline: left to right.

¹ No iodine contrast agent will be administered if deemed ineligible

² Only if subject has been treated with thrombolysis

Italics depicts standard diagnostic protocol

Subjects presenting with acute stroke will be evaluated by the physician in accordance with the institutional practice, to establish an appropriate treatment plan based on the subject's medical condition and available diagnostic screening procedures prior to recruitment in the Study. The 3rd inclusion criterion will define the investigational device exposure for the subjects:

3.I subjects will be imaged with DE-CBCT without and with contrast agent day 1 after standard diagnostic CT imaging. If subject is still hospitalized at Karolinska on day 2, an additional DE-CBCT without and with contrast agent will be made.

3.II subjects will be imaged with DE-CBCT without and with contrast agent day 2 directly after their standard diagnostic DECT scan.

3.III subjects will be imaged with DE-CBCT without and with contrast agent day 1 after standard diagnostic CT imaging.

Figure 4 provides an overview of the study flow, consisting of a combination of standard of care scans and scans with the NEXIS investigational device.

[figure not shown]

Figure 4. Study flow chart according to inclusion criterion met. Timeline: left to right.

IGT Systems	Clinical Research Protocol Next Generation X-ray Imaging System (NEXIS)	Doc ID: XCY612-130814 Rev: 01 Page 27 of 57
-------------	----------------------------------------------------------------------------	---------------------------------------------------

6.6. Subjects

6.6.1. Number of subjects

In total, the minimum sample size required is 20 subjects, of which two-thirds have ischemia, one-third have intracranial hemorrhage, and at least half must have done a contrast enhanced DE-CBCT. Our estimated necessary sample size is 29 subjects, taking algorithm optimization and potential invalid data into account.

The number of subjects are necessary to collect sufficient data for the evaluation of the primary and secondary endpoints, taking algorithm optimization and potential invalid data into account. Subjects will be replaced if they or the investigator withdraws the patient for any reason described in 6.4.1 or if image quality is too low due to movement during exam. The enrollment period is expected to last for 4-6 months.

See Section 8 ([Statistical considerations](#)) for more details on the subject sample size.

6.6.2. Procedure for the replacement of subjects

Subjects in the study will be replaced in case of withdrawal of consent or if subject is found ineligible for the study after signing of the informed consent and before the measurement. Subject will also be replaced if patient movement during image acquisition significantly affect assessment of the image material, as judged by the investigator. If only the second scan for subjects included according to 3.I is invalid, they will not be replaced.

6.6.2.1. Lost to follow-up

If a subject enrolled by inclusion criterion 3.I fails to return for their day 2 examination, their first study examination will still be included in the study. Thus, these subjects will not be replaced.

6.6.3. Inclusion and exclusion criteria

Subjects participating in the study will be carefully selected based on the next inclusion and exclusion criteria.

6.6.3.1. Inclusion criteria

1. The patient has signed and dated the Informed Consent Form (ICF)
2. Age \geq 50 years old
3. Clinical and radiological signs consistent with acute stroke
 - I. Patient diagnosed with ischemic stroke of the anterior circulation and not eligible for thrombectomy.
 - II. Patient diagnosed with ischemic stroke of the anterior circulation and subjected to thrombectomy.
 - III. Patient diagnosed with hemorrhagic stroke.

6.6.3.2. Exclusion criteria

1. Pregnant or breastfeeding women.
2. Previous stroke or parenchymal damage/defects in anterior circulation territories (only applicable for subjects included by criterion 3.I or 3.II).
3. Subject participates in a potentially confounding drug or device trial during the course of the study.
4. Participation in the study exposes the subject to risk, as assessed at the discretion of the treating physician.
5. All subjects who meet an exclusion criteria according to national law.
6. Subject or subject family member is a known Philips employee.

IGT Systems	Clinical Research Protocol Next Generation X-ray Imaging System (NEXIS)	Doc ID: XCY612-130814 Rev: 01 Page 28 of 57
-------------	----------------------------------------------------------------------------	---------------------------------------------------

6.7. Follow Up

Subject participation is terminated at the end of investigation day 1 (criterion 3.III) or day 2 (criterion 3.I and 3.II).

6.8. Adverse Events

Any adverse events that occur during the investigation (day 1 or day 2) will be recorded.

7. Adverse event reporting

The proposed study will be started under the MDD, however as of 26 May 2020, the reporting of serious adverse events and device deficiencies shall be carried out in accordance with the Medical Device Regulation.

Adverse event reporting under MDD is done according to ISO14155:2011 and MEDDEV 2.7/3 revision 3.

7.1. Definitions

Adverse Event (AE)

ISO14155: Any untoward medical occurrence, unintended disease or injury, or untoward clinical signs (including abnormal laboratory findings) in subjects, users or other persons, whether or not related to the investigational medical device

NOTE 1 This definition includes events related to the investigational medical device or the comparator.

NOTE 2 This definition includes events related to the procedures involved.

NOTE 3 For users or other persons, this definition is restricted to events related to investigational medical devices.

EU-MDR: An Adverse Event (AE) is defined as any untoward medical occurrence, unintended disease or injury or any untoward clinical signs, including an abnormal laboratory finding, in subjects, users or other persons, in the context of a clinical research, whether or not related to the investigational device.

Serious Adverse Event (SAE)

ISO14155: Adverse event that led to any of the following:

a) death

b) serious deterioration in the health of the subject, that resulted in any of the following:

- 1) a life-threatening illness or injury, or
- 2) a permanent impairment of a body structure or a body function, or
- 3) hospitalisation or prolongation of patient hospitalization, or
- 4) in medical or surgical intervention to prevent life-threatening illness or injury or permanent impairment to a body structure or a body function.

5) a chronic disease

c) foetal distress, foetal death or a congenital physical or mental impairment or birth defect

EU-MDR: Any adverse event that led to any of the following:

(a) death,

(b) serious deterioration in the health of the subject, that resulted in any of the following:

- (i) life-threatening illness or injury,
- (ii) permanent impairment of a body structure or a body function,
- (iii) hospitalisation or prolongation of patient hospitalisation,
- (iv) medical or surgical intervention to prevent life-threatening illness or injury or permanent impairment to a body structure or a body function,
- (v) chronic disease,

(c) foetal distress, foetal death or a congenital physical or mental impairment or birth defect

Device Deficiency

ISO14155: Inadequacy of a medical device with respect to its identity, quality, durability, reliability, safety or performance

NOTE Device deficiencies include malfunctions, use errors, and inadequate labelling.

IGT Systems	Clinical Research Protocol Next Generation X-ray Imaging System (NEXIS)	Doc ID: XCY612-130814 Rev: 01 Page 29 of 57
-------------	----------------------------------------------------------------------------	---------------------------------------------------

EU-MDR: Any inadequacy in the identity, quality, durability, reliability, safety or performance of an investigational device, including malfunction, use errors or inadequacy in information supplied by the manufacturer.

Adverse Device Effect (ADE)

ISO14155: Adverse event related to the use of an investigational medical device. Note This includes any adverse event resulting from insufficient or inadequate instructions for use, deployment, implantation, installation, or operation, or any malfunction of the investigational medical device, and any event resulting from use error or from intentional misuse of the investigational medical device.

Serious Adverse Device Effect (SADE)

MEDDEV 2.7/3 rev 3: Adverse device effect that has resulted in any of the consequences characteristic of a serious adverse event.

Unanticipated Serious Adverse Device Effect (USADE)

ISO14155: Unanticipated Serious Adverse Device Effect is a serious adverse device effect which by its nature, incidence, severity or outcome has not been identified in the current version of the risk analysis report

NOTE Anticipated serious adverse device effect (ASADE) is an effect which by its nature, incidence, severity or outcome has been identified in the risk analysis report.

7.2. Reporting

It is the responsibility of the Investigator to comply with 1) his/her Ethical Committee requirements for reporting safety event, and 2) any country specific regulatory/CA Investigator requirements for safety events.

All adverse events shall be recorded. The safety assessments will consist of Adverse Events (AE) from the time the ICF is signed through departure from study for those patients enrolled, and to discharge or 24 hours for those patients identified as screening failures by inclusion/exclusion criteria.

The AEs will be categorized using MedDRA Coding of Adverse Events Nomenclature Standardized nomenclature.

The investigator shall report to Sponsor any related or unrelated serious adverse (device) event and device deficiencies that could have led to a Serious Adverse Device Effect (SADE) if a) suitable action had not been taken or b) intervention had not been made or c) if circumstances had been less fortunate via the adverse event form or device deficiency form in the e-CRF. The investigator shall supply the Sponsor, upon Sponsor's request, with any additional information related to the safety reporting of a particular event. The investigator should report to the MEC and/or competent authority these serious adverse events and device deficiencies that might have led to a serious adverse device effect, if required by MEC or competent authority, as further detailed in Appendix IV.

The reporting requirement from investigational site to the sponsor is:

Type of Adverse Event	Reporting Requirements

 • SAE • SADE • USADE • Death • Any study device deficiency that could have led to an SADE 	Report to Sponsor immediately upon awareness of event but no later than 24 hours (In written within 5 days).

 • All other Adverse Events • All other study device deficiencies 	Report to Sponsor immediately upon awareness of event, but no later than 14 calendar days.

IGT Systems	Clinical Research Protocol Next Generation X-ray Imaging System (NEXIS)	Doc ID: XCY612-130814 Rev: 01 Page 30 of 57
-------------	----------------------------------------------------------------------------	---------------------------------------------------

Non-serious adverse (device) events shall be recorded on the adverse event forms. Device Deficiencies shall be recorded on the device deficiency form. The Sponsor and Monitor can request access to this information at any time. The event reporting is done via the electronic data capture system (EDC). If the electronic data capture system (EDC) is unavailable the AE can be notified via email to the study mailbox:

[REDACTED]

The study site personnel must seek information on Adverse Events by specific questioning and, as appropriate, by examination. Information on each Adverse Event should be recorded immediately in relevant source documents, and also on the appropriate eCRF (in the EDC). The following attributes must be assigned by the Investigator for adverse events:

- Description of the event
- Actions taken
- Date of onset and resolution
- Determination if event is serious
- Determination if the event is anticipated – in the event of an SADE
- Determination of event severity
- Determination of the causal relationship to study device and study procedure

Information collected for device deficiencies are:

- Date of device deficiency
- Whether this could have led to a Serious Adverse Device Effect (SADE) if
 - a) suitable action had not been taken or
 - b) intervention had not been made or
 - c) if circumstances had been less fortunate.

The clinical course of each event will be followed until resolution or stabilization.

The investigator shall supply the Sponsor, upon Sponsor's request, with any additional information related to the safety reporting of a particular event.

The investigator should report to the MEC and/or competent authority these serious adverse events and device deficiencies that might have led to a serious adverse device effect, if required by MEC or competent authority, as described below and summarized in Appendix IV: Reporting requirements to MEC and Competent Authority.

Adverse Events (AE) and Adverse Device Effects (ADE)

All adverse events shall be recorded. The safety assessments will consist of Adverse Events (AE) from the time the ICF is signed through departure from study for those patients enrolled, and to discharge or 24 hours for those patients identified as screening failures by inclusion/exclusion criteria.

The AEs will be categorized using MedDRA Coding of Adverse Events Nomenclature Standardized nomenclature.

The sponsor is:

- Responsible for the classification of adverse events and ongoing safety evaluation of the clinical research and shall review the investigator's assessment (done by the CEC) of all adverse events and determine and document in writing their seriousness and relationship to the investigational device; in case of disagreement between the sponsor and the principal investigator(s), the sponsor shall communicate both opinions to MEC and Competent authorities
- Review all device deficiencies and determine and document in writing whether they could have led to a serious adverse device effect; in case of disagreement between the sponsor and the principal investigator(s), the sponsor shall communicate both opinions to MEC and competent authority.
- Report or ensure the reporting, to the MEC by the principal investigator(s), of all serious adverse events and device deficiencies that could have led to a serious adverse device effect,

IGT Systems	Clinical Research Protocol Next Generation X-ray Imaging System (NEXIS)	Doc ID: XCY612-130814 Rev: 01 Page 31 of 57
-------------	----------------------------------------------------------------------------	---------------------------------------------------

- In case of serious adverse device effects and device deficiencies that could have led to serious adverse device effects, determine whether the risk analysis needs to be updated and assess whether corrective or preventive action is required.

Competent Authorities:

The Sponsor shall report immediately, but no later than 2 calendar days after awareness by sponsor of a new reportable event or new information in relation with an already reported event to the competent authorities the following Serious Adverse events and device deficiency that occur at any of the involved trial sites:

- Serious Adverse Events and
- Device Deficiencies that could have led to a Serious Adverse Device Effect (SADE) if
 - a) suitable action had not been taken or
 - b) intervention had not been made or
 - c) if circumstances had been less fortunate

A causal relationship between the SAE and the investigational device(s), or procedures performed as part of the clinical trial or other conditions of the trial conduct cannot be excluded.

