3.III subjects will be imaged with DE-CBCT without and with contrast agent day 1 after standard diagnostic CT imaging.

The figure below provides an overview of the study flow, consisting of a combination of standard of care scans and scans with the NEXIS investigational device.

[figure not shown]

Figure 1: Study flow chart according to inclusion criterion met. Timeline: left to right.

Follow up

Patient departs from the investigation at end of investigation day 1 (group III) or day 2 (group I and II).

Duration of the study

The total duration of the study is expected to be 4-6 months for subject recruitment and investigation

2. State of the art in stroke treatment

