In order to evaluate relevant diagnostic quality and image quality in the acute stroke setting, we will include subjects with ischemic stroke of the anterior circulation coming to the comprehensive stroke center at Karolinska University Hospital (inclusion criteria 3.I and 3.II). As initial imaging must be able to identify or exclude intracranial hemorrhage, subjects determined to have a hemorrhagic stroke will also be included in the study (3.III). For stroke patients, an additional contrast enhanced scan is relevant to delineate the intracranial vessels in order to identify relevant pathology.

Even though no additional radiation dose compared to a standard CBCT is anticipated, subjects will receive an additional radiation dose compared to standard diagnostic protocol due to the additional image acquisition. However, the brain is quite insensitive to radiation exposure (weighting factor of 0.01

IGT Systems	Clinical Research Protocol Next Generation X-ray Imaging System (NEXIS)	Doc ID: XCY612-130814 Rev: 01 Page 23 of 57
-------------	----------------------------------------------------------------------------	---------------------------------------------------

when calculating effective organ doses (29), and sensitivity to stochastic radiation effects decreases with age (30). The great majority of stroke patients in Sweden are 65 years or older (31). To ensure that the risks of additional radiation is minimized, no subject under the age of 50 will be included in the study. No gender specific safety considerations have been identified for subjects aged 50 and over. However unlikely, women included in the study will be asked about current pregnancy.

Usage of iodine contrast agents poses a small risk of contrast-induced acute kidney injury (CI-AKI). We will follow Swedish national guidelines, recommending that the total amount of iodine (in grams) administered for a contrast enhanced scan should not exceed the calculated aGFR in mL/min (32), given that the patient has a sufficient renal clearance and does not have multiple risk factors. For more information, see section 6.2.3.

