6.2.3. Iodine contrast agent eligibility test

Kidney function by means of aGFR and non-renal risk factors for CI-AKI will be determined day 1 (criteria 3.I and 3.III) and/or day 2 (3.I and 3.II), before imaging with the investigational device.

Sufficient renal clearance is determined as aGFR equal to or over 45 ml/min. Non-renal risk factors for CI-AKI are determined as diabetes, chronic heart failure (NYHA III/IV), dehydration, sepsis, hypoxia, liver cirrhosis and regular intake of NSAID or nephrotoxic substances such as antibiotics, chemotherapy and immunosuppressive agents.

A sufficient renal clearance and absence of multiple non-renal risk factors for CI-AKI will be required to perform contrast enhanced scans according the following dosage (32): Gram iodine / GFR ratio $\leq 1,0$. This dosage ratio also applies for consecutive scans with iodine contrast agent, such as day 1 subjects included by criterion 3.I (already investigated with standard of care mCTA and CTP).

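### For most contrast schedules, adverse event collection closes on the day of the last study contrast injection and no aGFR is scheduled after it, so the safety tables say little about delayed, non-serious contrast effects

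*Combined protocol and SAP*

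**What the plan says.** Section 7.2 sets the adverse event window from signature of the consent form "through departure from study for those patients enrolled, and to discharge or 24 hours for those patients identified as screening failures". The same rule appears a second time in 7.2, under the paragraph on adverse events and adverse device effects. Section 6.8 restates it: "Any adverse events that occur during the investigation (day 1 or day 2) will be recorded".

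Departure is fixed in 6.7, and in the same terms under Follow up in the Summary: "Subject participation is terminated at the end of investigation day 1 (criterion 3.III) or day 2 (criterion 3.I and 3.II".

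Contrast timing is in 6.5. For the thrombectomy group: "3.II subjects will be imaged with DE-CBCT without and with contrast agent day 2 directly after their standard diagnostic DECT scan". For the hemorrhage group: "3.III subjects will be imaged with DE-CBCT without and with contrast agent day 1 after standard diagnostic CT imaging". Subjects in 3.I are scanned on day 1 and, if still hospitalized, again on day 2, each time with contrast if eligible.

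Renal testing is in 6.2.3: "Kidney function by means of aGFR and non-renal risk factors for CI-AKI will be determined day 1 (criteria 3.I and 3.III) and/or day 2", in each case ahead of the investigational scan. Tables 1 and 3 show the same order. No post-injection renal test appears there or among the variables in section 8.

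Section 5.5 names contrast-induced acute kidney injury as a small risk of the iodine agent. Table 4 in 7.3 lists side effects of the additional contrast as an anticipated adverse device effect. Section 8.10.2 sets out to report every adverse event, and 8.10.3 tabulates the device effects.

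**The concern.** Section 4 limits the risks of the study procedures to X-ray dose and iodine contrast, and says that patients gain no direct benefit. For the contrast risk, the plan records the exposure (iodine dose, 8.10.1) but schedules no matching renal outcome after the last injection. A renal change is mainly a laboratory finding, and 7.1 counts abnormal laboratory findings as adverse events. Such a finding can only be recorded if a sample is taken and someone looks at it while collection is open.

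An empty renal row in the final tables could therefore mean that nothing happened or that nothing was measured. The tables would not let a reader tell which.

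**Working it through.** The plan gives no figure to reproduce, and the point depends on no sample size, power or alpha. The check sets three times side by side for each group: the last study injection (6.5, Tables 1 and 3), the close of adverse event collection (7.2, 6.7, 6.8), and any aGFR scheduled after that injection (6.2.3, Tables 1 and 3).

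| Group and contrast schedule | Last study injection | Collection closes | Further days | Scheduled aGFR after last injection |
|---|---|---|---|---|
| 3.III | day 1 | end of day 1 | 1 - 1 = 0 | none |
| 3.II | day 2 | end of day 2 | 2 - 2 = 0 | none |
| 3.I, injected on day 2 | day 2 | end of day 2 | 2 - 2 = 0 | none |
| 3.I, injected on day 1 only | day 1 | end of day 2 | 2 - 1 = 1 | one, if the day 2 eligibility test is done |

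The last row is the exception. For a 3.I subject injected on day 1 and tested again on day 2, the second eligibility test doubles as a later value for the first injection. If that subject is then injected on day 2, the third row applies to the second injection.

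Three other provisions might fill the gap:

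1. Events are followed to resolution or stabilization (7.2). This applies to events already found, and so does not help to find one after departure.
2. Staff must seek events by questioning and, where appropriate, by examination (7.2). This can pick up symptoms on the day. It schedules no laboratory test, and the duty falls within the same window.
3. Serious events that the investigator learns of after departure are reported if considered related to the investigational system (Appendix IV). This route is passive and leaves out non-serious events.

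None of the three yields a planned renal observation after the last injection in the first three rows.

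**The case against.** The case on the other side has several parts.

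- **Prevention.** Section 6.2.3 handles the renal risk beforehand: aGFR of at least 45 ml/min, no multiple risk factors, and a gram iodine to GFR ratio of at most 1.0, also across consecutive scans. This stands as risk control. It does not tell a reader whether the control worked.
- **Descriptive aims.** Sections 8.10.2 and 8.10.3 have no performance requirement. This stands, and is why the point is minor.
- **Reporting routes remain.** A reader might infer that the tables can show no renal harm at all. That goes too far. A same-day event would be recorded, and a related serious event learned of later would be reported.
- **Appendix IV.** A reader might infer that contrast injury falls outside its post-departure rule. Table 4 lists contrast side effects among the device effects, so the wider reading is the more natural one. A clarification is optional.
- **Screening failures.** A reader might infer that they are followed longer than contrast-exposed subjects. The text does not say whether the earlier or the later of discharge and 24 hours applies, and the end of a day is undefined. The comparison has no bearing on renal detection in any case.
- **Section 4.** Its conclusion that the contrast risk is justified is a pre-study assessment that points to the Investigator Brochure. It does not rest on these tables.

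**Conclusion.** The point holds as a minor gap in safety data collection. No subject has a scheduled renal value after a day 2 injection, and no 3.III subject has one after the day 1 injection. In these subjects collection also closes on the day of injection. The tables are therefore largely uninformative about delayed, non-serious contrast effects. No primary or secondary endpoint is touched.

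The same-day close rests on reading day as the day of investigation, which the plan does not define further. A reading of day as 24 hours would lengthen the window but add no renal test.

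A reader might want to go on to a percentage of events missed, an upper limit for the true rate, or a minimum share of subjects without a later aGFR. The documents support none of these. They give no onset time for contrast-induced kidney injury and no split between 3.I and 3.II. They do not require contrast in everyone: 5.5 allows scans without it, and 8.2 asks for it in at least half of the minimum sample. Nor is the hemorrhage third in 8.2 the same as group 3.III, because 8.8.3 also covers hemorrhagic transformation of ischemic stroke.

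**What to change.** For contrast-exposed subjects, extend adverse event collection by chart review to 72 h after the last study injection or to discharge, whichever is first. The 72 h is a practical choice; the 72 h iodine look-back in 8.5.1 is a baseline item and does not justify it. In the same review, record any routine-care creatinine or aGFR. Section 6.3 already provides for standard-of-care parameters to be accessed retrospectively.

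Wording to align:

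- 7.2 (both places), 6.8 and the Summary: the new window.
- 6.7: chart review continues after the last study procedure.
- 8.10: a listing by subject of the aGFR before injection, any later value with its time, and the iodine dose, plus the number of subjects without a later value. This is descriptive only.
- Appendix IV, optionally: the investigational system includes study procedures and contrast.

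The cost is a chart review in a study planned at 29 subjects and a few e-CRF fields, with no new visit or blood test. There are downsides. Subjects discharged early or without a routine sample stay unobserved. More events from the stroke itself will be recorded. Study contrast cannot be separated from standard-of-care contrast. The change may also need ethics committee and competent-authority authorization under section 10.

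If the window is kept, add one sentence to 8.10.2 and 8.10.3 stating that the tables do not address renal effects arising after the day of the last injection.
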